## **Objective**

We describe the first evaluation of the VA's automated texting system (aTS). Consistent with an implementation-effectiveness hybrid 2 study design, our aims were to: (1) qualitatively and quantitatively assess implementation outcomes for the aTS; and (2) assess impact of the aTS on HCV clinical outcomes in a real-world setting.

## **Methods**

Our evaluation was guided by the Practical, Robust, Implementation and Sustainability Model (PRISM), which defines a set of factors for consideration when designing, implementing, sustaining and evaluating interventions.i PRISM posits that the extent to which an intervention achieves results can be linked to the four PRISM domains, namely the intervention's characteristics (via patient and organizational perspectives), the intervention recipients (via patient and organizational perspectives), the external environment, and the implementation and sustainability infrastructure.

## **Design**

This was a multi-site, mixed-methods, randomized, two-group hybrid type 2 study design comparing the effectiveness of usual implementation (UI) and augmented implementation (AI).ii Matched comparison (i.e., no intervention) sites helped to determine effectiveness of the aTS in aiding HCV treatment. The study was reviewed by the Institutional Review Board (IRB) at the Edith Nourse Rogers Memorial Veterans Hospital in Bedford, Massachusetts and determined to be a quality improvement study (VA Handbook 1058.05).iii The project was conducted from February 2017 through February 2018.

## **Setting & Participants**

The group of clinics selected reflects a purposive sample based on several criteria, including clinic size and complexity, and geography. HCV clinics were recruited via a national HCV provider email listserv and monthly HCV provider phone call. The seven HCV clinics selected were randomly assigned to either UI or AI, using set randomization, which, with small sample sizes, helps to achieve balance on a set of relevant characteristics – in this case, urban/suburban setting and on HCV patient volume.iv Two additional comparison clinics were selected purposively because they had similar patient volume, clinic complexity, and geographic locale to the other participating clinics.v Thus in total, data were collected from nine VA clinics: four AI clinics, three UI clinics, and two comparison clinics. Care teams within the HCV clinics had different compositions and involved pharmacists, nurse practitioners, registered nurses, and social worker to varying degrees.

## **Intervention: Text Messaging for HCV treatment**

At the time of implementation, usual care for HCV included starting a patient on daily oral medication for 8-16 weeks, and follow-up in-person visits, blood lab work, and medication refills at 2- or 4-week intervals. The aTS for HCV was intended to improve processes and outcomes of care, and satisfaction with care. The HCV texting protocol included reminder text messages about medication taking, appointment keeping, and laboratory completion, and motivational text messages to encourage continued engagement in treatment. To be consistent with the standard treatment processes, each of the seven clinics worked collaboratively with study team members (VY, KM, and national aTS program office) to tailor the HCV texting protocol to align with their clinic's workflow (e.g., adjusting messaging logic from 2 to 4 weeks for different treatment intervals). Motivational messages were supportive in nature and intended to promote self-management and increase feelings of connection to the treatment team.

Message content could be tailored for content (e.g., adding clinic name and phone number) and timing (e.g., adjusting time of day that medication reminder is sent) through patient and provider discussion at the time of aTS enrollment, or later to reflect patient preferences. Veterans who did not use the aTS received otherwise standard HCV care.

### ***Usual Implementation Facilitation and Augmented Implementation Facilitation***

Facilitation was employed to support adoption of the aTS at participating clinics, with facilitation delivered by a primary (VY) and a secondary (KM) external facilitator. During the four-month *pre-implementation* phase, the functions of the external facilitators included engaging local, regional and national stakeholders to garner support for the aTS. The *implementation* phase took place over six months and differed between usual implementation (UI) and augmented implementation (AI), as detailed below. The *post-implementation* (evaluation) phase took place over three months.

**UI clinics:** UI clinics received the start-up experience that VA designed for all new clinics instituting the aTS. This involved a live virtual demonstration of the aTS, and access to an aTS resource website that included promotional materials and training guides. UI clinics could receive troubleshooting assistance from the external facilitators by phone or email, but only if and when they reached out to the them.

**AI clinics:** In addition to the start-up experience for UI sites described above, AI clinics received an implementation toolkit, support for local champion development, and proactive outreach by the primary external facilitator. The toolkit was developed by our team based on a formative evaluation that involved visits to 5 VA medical centers around the country to conduct interviews with patients and clinical staff who were using a pilot version of the aTS for conditions other than HCV. The toolkit contained sections on evidence of texting in healthcare, gaining leadership and clinic support for technology like the aTS, use of champions to support aTS adoption, tips and tools on how to use the aTS, and aTS promotional materials to encourage clinic and patient participation. Each AI clinic received one in-person visit from the primary external facilitator early in their implementation efforts. Additionally, the primary external facilitator-initiated check-ins with AI clinic champions throughout implementation.

Facilitation was delivered via email, phone, and in-person. In the pre-implementation period, to establish rapport and trust, there was more emphasis on phone calls and in-person meetings, whereas during implementation, those modes were used less while use of emails increased. Facilitation calls lasted from 5 minutes to 90 minutes (40-minute average) and site visits by the external facilitator lasted two to four hours. The most common facilitation strategies employed were local technical assistance, assessing for readiness, site visits, identifying and preparing champions, developing and distributing educational materials, building a coalition, and tailoring implementation to context.vi,vii The template for intervention description and replication (TIDieR) checklist was used to guide intervention description (Additional File 1).viii

### ***Measures and Data Collection***

PRISM domains (implementation and sustainability infrastructure, intervention characteristics, recipients via both patient and organizational perspectives, external environment) guided the measures and data collection and are denoted in parentheses.

**Implementation Processes: Facilitation (Implementation and Sustainability Infrastructure).** The external facilitator (VY) logged facilitation events on a tracking sheet, including facilitation date, length of time, mode of delivery (i.e., email, phone call, or in-person visit), purpose, notes, and other observations. From the perspective of the primary facilitator, if multiple facilitation events occurred in one day, only one event per person, per day was counted.

**Implementation Outcomes: Texting Use (Intervention).** Providers logged the number of patients who were offered the aTS and noted whether patients enrolled or declined, including the reason for declining. The content of patient text message replies was extracted from the aTS portal. To be eligible for the texting protocol, patients had to be starting HCV medication treatment. There were four steps to initiate a patient on the aTS: (1) providers verbally offered patients the aTS, (2) providers registered interested patients in the aTS portal and assigned them the HCV protocol, and (3) once a patient was registered, the aTS would send an automated text message requesting the patient authenticate themselves by replying to this initial text message thus prompting the assigned HCV protocol to begin, and (4) patients actively text with the aTS.

**Clinical Effectiveness Outcomes.** Medication adherence was measured via patient text response rate, operationalized as the number of days of text-confirmed medication taking divided by the number of days

receiving medication reminder texts. Consistent with other adherence standards, an affirmative text response rate of  $\geq 80\%$  was considered high adherence.ix Clinical data, including HCV treatment regimen and duration, and lab dates and results, were extracted from VA's National HCV Dashboard with data from VA's Corporate Data Warehouse.x The goal of treatment is to achieve cure, or sustained virologic response (SVR), where there is an undetectable HCV lab result 12 weeks after completion of treatment.

*Questionnaires (Recipients, intervention, implementation).* Patients at each clinic completed baseline and follow-up (after 8-12 weeks of using the aTS) questionnaires. The comparison clinics followed the same schedule, though without any use of texting. Patient questionnaires covered the topics of self-rated health status, adherence, illness perception, health engagement and activation, technology use, experiences with the aTS (usability, usefulness, working alliance), and demographics.xi,xii,xiii,xiv,xv,xvi Provider questionnaires followed the same schedule and covered topics of technology experience, quality improvement culture, climate and readiness for implementation, satisfaction with current local HCV care processes, experiences with the aTS (usability and usefulness), and demographics.xvii,xviii,xix,xx Questionnaires were pre-tested for clarity, redundancy, and relevancy by two patients and four providers and implementation scientists independent of the study team.

For effectiveness outcomes measures, we combined patients who were using the aTS regardless of whether they were in UI or AI clinics. These were referred to as “texters”. In contrast, “non-texters” could come from UI or AI clinics (patients who agreed to participate in the project but never completed the last step of authenticating themselves with the aTS, and thus never received any text messages), as well as from the two comparison clinics that did not implement the aTS.

*Semi-structured interviews (all PRISM domains).* Qualitative semi-structured telephone interviews were conducted with patients and providers who used or were invited to use the aTS. Interviews were conducted in the follow-up period during September and October 2017. The interview guides were informed by PRISM domains (denoted in parentheses) and explored issues regarding barriers to and facilitators to aTS uptake and use (intervention; implementation and sustainability), usability and usefulness of the aTS (intervention), and how the aTS was experienced by patients and providers (recipients) in the course of treatment and daily practice (external environment). Interviews were conducted by members of the study team not involved in facilitation (BP, CG) and lasted about 30 minutes.

For each questionnaire or qualitative interview completed, patients received a \$10 store gift card to compensate them for their time.

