### **Data Analysis**

Descriptive and bivariate analyses of facilitation log data were conducted to compare facilitation dose, comparing UI and AI implementation groups. Descriptive and bivariate analyses were conducted on provider and patient questionnaires, text message frequencies, and clinical data to assess differences between implementation groups (UI and AI) in implementation outcomes. We then compared clinical effectiveness outcomes between texters and non-texters. We examined patient progression through the aTS initiation process, by calculating the percent retained from one step to the next, by UI and AI implementation group. Chi-square tests were used to assess differences between the two groups. All analyses were conducted in RStudio Version 1.0.153 and statistical significance was defined as  $p < 0.05$ .xxi

Qualitative interviews were audio recorded, transcribed verbatim, and then analyzed using NVivo 11 software.xxii Thematic analysis of all qualitative data (interview transcripts, meeting notes, text messages) was conducted.xxiii PRISM domains provided the deductive *a priori* codes and other codes emerged with inductive coding. The triangulation of quantitative and qualitative data served as a final step of analysis.

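### Patient ratings of aTS usability and usefulness can in practice come only from users, a group formed after clinics were randomised, so a UI-AI significance test on them does not test an effect of AI

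*Combined protocol and SAP*

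**What the plan says.** Setting & Participants fixes the randomised unit: "The seven HCV clinics selected were randomly assigned to either UI or AI, using set randomization" (four AI clinics and three UI clinics).

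Under Measures and Data Collection, a patient becomes a user in four later steps: the provider offers the system, registers patients who are interested, the patient authenticates by reply, and the patient texts. Some participants in UI and AI clinics "never completed the last step of authenticating themselves with the aTS, and thus never received any text messages".

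The same section says of the questionnaires: "Patients at each clinic completed baseline and follow-up (after 8-12 weeks of using the aTS) questionnaires". Patient topics include "experiences with the aTS (usability, usefulness, working alliance"; provider topics include "experiences with the aTS (usability and usefulness".

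Data Analysis states: "Descriptive and bivariate analyses were conducted on provider and patient questionnaires, text message frequencies, and clinical data to assess differences between implementation groups", meaning UI and AI, in implementation outcomes. Significance is p < 0.05. The section also compares UI and AI on the percentage retained from each initiation step to the next.

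The section on usual and augmented facilitation says that facilitation was there to support adoption. Only AI clinics received the toolkit, champion support, a site visit and proactive outreach.

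The plan does not say who was asked the aTS-experience items, how non-users are handled on them, or whether any adjustment is made for selection into use.

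**The concern.** Randomising clinics protects a UI-AI comparison when every patient in the clinics, or a group fixed before randomisation, contributes an outcome. A usability rating needs a user. Users emerge after randomisation, are selected by providers and by themselves, and their number is something that AI is meant to change.

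If AI raises uptake, its users include patients who would not have become users under UI. If those patients would rate the system differently, mean ratings differ between arms although no patient's experience has changed. A strategy that succeeds on uptake could then be reported as worse on usability or usefulness, or as better if the additional users were keener. A reader who knows that clinics were randomised would take the p-value as evidence about AI.

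**Working it through.** **Inputs from the documents.** Seven clinics randomised (4 AI, 3 UI); use begins after randomisation; UI-AI analyses of questionnaires are bivariate; threshold p < 0.05. There is no uptake rate, rating SD, patient number or power statement, so there is no plan figure to reproduce. Every number below is an assumption chosen to show a range.

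**Model.** Let willingness to use be standard normal. A patient becomes a user when willingness exceeds the cut-off c that gives uptake u. Ratings have SD 1 and correlate ρ with willingness. AI has no effect on any patient's rating. Then

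- mean rating among users = ρ × λ(u), with λ(u) = φ(c)/u and c = z(1 − u);
- spurious AI − UI gap = ρ × [λ(u_AI) − λ(u_UI)].

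**One case in full.** Take uptake of 20% in UI and 40% in AI, with ρ = 0.4.

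- UI: c = 0.842, φ = 0.280, λ = 0.280/0.20 = 1.400.
- AI: c = 0.253, φ = 0.386, λ = 0.386/0.40 = 0.966.
- Gap = 0.4 × (0.966 − 1.400) = −0.17 SD.

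**Range of gaps (SD units), true effect zero.**

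| Uptake UI v AI | ρ = 0.2 | ρ = 0.4 | ρ = 0.6 |
|---|---|---|---|
| 20% v 40% | −0.09 | −0.17 | −0.26 |
| 30% v 50% | −0.07 | −0.14 | −0.22 |
| 40% v 60% | −0.06 | −0.13 | −0.19 |
| 50% v 80% | −0.09 | −0.18 | −0.27 |
| 50% v 50% | 0 | 0 | 0 |

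The gap is also zero at ρ = 0 and changes sign if ρ is negative. Dividing by the users' own, slightly smaller SD takes the largest value to −0.30.

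**Chance of p < 0.05** (two-sided, normal approximation, patients treated as independent, user numbers proportional to uptake). In the worked case, the users' variance 1 − ρ²λ(λ − c) is 0.875 in UI and 0.890 in AI, so the average SD is 0.94 and the standardised gap is 0.174/0.94 = 0.185. With 100 UI and 200 AI users, the gap over its standard error is 0.185/√(1/100 + 1/200) = 1.51. The chance is Φ(1.51 − 1.96) + Φ(−1.51 − 1.96) = 0.33. Across the four unequal-uptake rows at ρ = 0.4, it is 18% to 33% with 100 UI users and about 12% to 19% with 50, against a nominal 5%.

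**A cruder two-type illustration.** Suppose ready users score 80 on a 0-100 scale in both arms, SD 15, with 30 users in UI and the additional AI users scoring lower.

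| AI users | Additional users' score | AI mean | Gap | z |
|---|---|---|---|---|
| 45 | 60 | (2400 + 900)/45 = 73.3 | −6.7 | −1.89 |
| 60 | 60 | (2400 + 1800)/60 = 70.0 | −10 | −2.98 |
| 45 | 70 | (2400 + 1050)/45 = 76.7 | −3.3 | −0.94 |
| 60 | 70 | (2400 + 2100)/60 = 75.0 | −5 | −1.49 |

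Here z = gap/(15 × √(1/30 + 1/n_AI)). Only the second row passes 1.96. It needs a doubling of uptake and a deficit of 20/15 = 1.33 SD among the additional users.

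**The case against.** **The test is permitted, not specified.** The only measure headed as an implementation outcome is texting use, and usability and usefulness are never named as UI-AI endpoints. That is correct. But the Data Analysis sentence covers the patient questionnaires without exclusion, so the comparison falls within the plan as written.

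**That only users can rate is an inference.** The plan does not say who received these items. The follow-up timing, counted in weeks of use, supports the inference strongly, and a patient who was never texted has no usability to report. The limit does matter for working alliance, which a non-user might be able to rate. The point therefore rests on usability and usefulness.

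**A reader might infer that AI will score worse because it reached more reluctant patients.** The documents do not support that. The AI toolkit includes "aTS promotional materials to encourage clinic and patient participation", but UI clinics also had promotional materials, through the resource website. What is distinctive about AI acts largely on clinics and providers. If it mainly increases offers to equally willing patients, the additional users need not differ and the bias shrinks towards zero. If they are keener, the sign reverses.

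**The size depends on unsupported inputs.** This stands. With 30 UI users, the model gives about 9% to 13% false positives at ρ = 0.4 (20% v 40% and 40% v 60% uptake) and 6% to 7% at ρ = 0.2.

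**It is a quality-improvement evaluation with interviews.** The interviews also explore experience of the system, which lowers the stakes, but they do not make the p-value interpretable.

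**Conclusion.** The concern holds in a limited form. Data Analysis allows UI-AI significance tests on patient usability and usefulness ratings that, in practice, only post-randomisation users can supply, and randomising clinics does not protect that comparison. Bias requires both that uptake differs by arm and that willingness to use is related to rating. The plan gives no reason to rule out either, and its direction cannot be settled beforehand.

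Under the assumed values, the spurious gap runs from zero to about 0.3 SD; the 0.67 SD gap (10/15) in the most extreme two-type case should not be taken as typical. The argument is clearest for patients. Providers also rate the system, but they are fewer and AI works on them directly. The consequence is confined to how these ratings may be interpreted; it does not undermine the comparison of uptake or the study as a whole.

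**What to change.** In Data Analysis, state that patient ratings of aTS usability and usefulness are reported by arm descriptively, without a UI-AI significance test. Beside them, show for each arm the number of raters and the number of patients offered the system, and compare raters' baseline characteristics by arm. State under Measures and Data Collection who was asked these items.

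Keep UI-AI testing for outcomes defined on all offered patients, such as uptake from the provider log. Because the offer itself follows randomisation, also show the number of eligible patients starting treatment where it can be obtained.

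Do not substitute a composite such as active texting plus a favourable rating, with non-users counted as failures. It would largely repeat uptake, which is already compared by arm, and it needs a cut-off for a favourable rating, a denominator and a rule for missing follow-up that the plan does not contain.

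The cost is a few sentences of analysis text, a small table, and one fewer set of p-values. The rater counts, offer log and baseline questionnaires are already part of the planned data.

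### Texter status depends on a reply made after registration, with no time window, so early treatment stoppers can collect among non-texters and tilt SVR toward the aTS

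*Combined protocol and SAP*

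**What the plan says.** Under Measures and Data Collection, patients become eligible when they begin treatment: "To be eligible for the texting protocol, patients had to be starting HCV medication treatment". The provider offers the aTS and registers the patient. Then "once a patient was registered, the aTS would send an automated text message requesting the patient authenticate themselves by replying". Active texting is listed as a fourth step.

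For effectiveness, the same section says "we combined patients who were using the aTS regardless of whether they were in UI or AI clinics"; these are the texters. Non-texters come from two sources. At UI and AI clinics they are "patients who agreed to participate in the project but never completed the last step of authenticating themselves with the aTS". The rest come from comparison clinics: "as well as from the two comparison clinics that did not implement the aTS".

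The clinical effectiveness paragraph names two outcomes: adherence measured from text replies, and SVR, assessed 12 weeks after treatment ends. The first cannot be calculated for patients who receive no texts, so SVR is the one available in both groups.

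Data Analysis then states: "We then compared clinical effectiveness outcomes between texters and non-texters". The methods described are descriptive and bivariate. The documents give no classification window, landmark or time-dependent exposure, no adjustment, and no rule for how early stoppers enter the SVR denominator.

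**The concern.** Group membership is settled by something the patient does after registration, and possibly after the first dose. A patient who stops treatment first, and does not reply afterwards, can only be a non-texter. A patient who replies in week 3 is a texter for the whole course, including the weeks in which they had to stay engaged in order to reply. This is the immortal-time problem. It needs no difference in prognosis between repliers and non-repliers, so adjustment for baseline covariates would not remove it.

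Texters versus non-texters is the clinical effectiveness comparison that Data Analysis describes for the second aim. A texter advantage on SVR could be read as an effect of the aTS when part of it comes from the classification rule.

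**Working it through.** The documents give no sample size, SVR rate, stopping rate or reply delay, so there is no figure of the plan's own to reproduce. Both models below assume that texting has no effect and that a patient who stops before replying never replies. From the documents come the 8 to 16 week treatment course, the seven aTS clinics and two comparison clinics, and the pooling of non-texters. All other inputs are assumptions.

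**Model 1: early stopping concentrated in the first 28 days.** A share w = 0.70 would eventually reply. A share q = 0.05 stop, evenly over 28 days, and none are cured; SVR is 95% in everyone else. Reply delay is uniform over 0 to L days. Comparison-clinic patients number 2/7 of aTS-clinic patients.

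- Chance that an early stopper stops before replying: f = (L/2)/28. For L = 28, f = 0.5.
- Texters: w(1 − qf) = 0.70 × 0.975 = 0.6825. Cured: 0.70 × 0.95 × 0.95 = 0.6318. SVR 92.6%.
- Non-texters at aTS clinics: 0.30 + 0.70 × 0.05 × 0.5 = 0.3175. Cured: 0.30 × 0.95 × 0.95 = 0.2708. SVR 85.3%.
- All non-texters, as the plan pools them: add 0.2857 patients, of whom 0.2857 × 0.9025 = 0.2579 are cured. SVR = 0.5286/0.6032 = 87.6%.
- Spurious advantage: **4.9 points pooled** (7.3 within aTS clinics alone).

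The same formulas give these pooled differences, in points:

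| Reply spread over | 5% stop in first 28 days | 5% stop over 84 days, f = (L/2)/84 |
|---|---|---|
| 28 days | 4.9 | 1.65 |
| 14 days | 2.5 | 0.82 |
| 7 days | 1.2 | 0.41 |
| 1 day | 0.2 | 0.06 |

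With 2% stopping in the first 28 days, the 28-day figure is 2.0.

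**Model 2: stopping at a constant rate over 84 days.** A share d stop, at rate λ = −ln(1 − d)/84. Reply delay is exponential with mean m days, so μ = 1/m. SVR is 95% in completers and 30% in stoppers; 30% never reply, for reasons unrelated to prognosis; comparison-clinic patients number half of aTS-clinic patients.

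- Stop before replying: λ/(λ + μ) × (1 − e^(−84(λ + μ))). For m = 28 and d = 0.10 this is 0.0324. A further e^(−84/m) × (1 − d) = 0.0448 complete without having replied.
- Texters among would-be repliers: 1 − 0.0324 − 0.0448 = 0.9228, of whom 0.10 − 0.0324 = 0.0676 stop. SVR = (0.0676 × 0.30 + 0.8552 × 0.95)/0.9228 = 90.2%.
- Non-texters at aTS clinics: 0.30 + 0.70 × (0.0324 + 0.0448) = 0.3541, SVR 85.3%. Pooled with 0.5 at 88.5%: 87.2%.
- Spurious advantage: 3.05 points.

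| Mean reply delay | Pooled advantage, d = 2% to 10% |
|---|---|
| At or before first dose | 0.00 |
| 1 day | 0.03 to 0.14 |
| 3 days | 0.09 to 0.41 |
| 7 days | 0.20 to 0.96 |
| 14 days | 0.39 to 1.87 |
| 28 days | 0.65 to 3.05 |

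With 100 texters, the chance that a chi-square test favours texters rises from 0.025 to 0.029–0.040 at 7 days and 0.038–0.104 at 28 days. The result also depends on SVR in stoppers: at 7 days and d = 5%, the advantage is 0.72 points if none are cured, 0.49 at 30%, 0.27 at 60%, and zero if they do as well as completers.

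These figures illustrate size and are not bounds. The 4.9 belongs to 5% stopping in Model 1; a higher rate there would exceed it.

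**Landmark check.** In Model 1 with L = 28, among patients still on treatment at day 14, whether a patient has replied is unrelated to later stopping. Both groups have SVR 0.95 × 0.95/(0.95 + 0.05 × 0.5) = 0.9025/0.975 = 92.6%, so the artefact is gone.

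**The case against.** A reader might infer that every patient who stops early becomes a non-texter and that texters are assured of an advantage. The documents do not support that. It needs three facts that they leave open: that replies came after the first dose, that stoppers did not still reply, and that stoppers remain in the SVR denominator. If any one fails, the artefact is zero. Nothing bars a late reply, and SVR is defined relative to completing treatment with no stated rule for non-completers.

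The 7.3-point figure is also tempting, but it leaves out the comparison-clinic patients whom the plan pools with the other non-texters. It also assumes replies spread over 28 days. The documents mention "follow-up in-person visits, blood lab work, and medication refills at 2- or 4-week intervals", but that schedule governs visits, laboratory work and refills. Authentication is a reply to an automatic message and needs no visit, so short delays are plausible. At a mean delay of a week or less, Model 2 gives under 1 point.

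Self-selection may matter as much. In the Model 2 setting, if replies are immediate but never-repliers stop twice as often, texters lead by 0.56 to 2.81 points pooled, with no timing artefact at all. A landmark does not touch that.

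These objections limit the size and certainty of the point. They do not remove it: the rule has no window, and nothing shows that the delay was zero.

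**Conclusion.** The point holds in conditional form. As written, the classification can create a spurious SVR advantage for texters if some patients stop before replying, do not reply later, have lower SVR and are kept in the denominator. The advantage in the pooled comparison is zero for replies at or before the first dose, about 0.2 to 1.2 points for delays of about a week, and about 0.65 to 4.9 points for delays of up to about four weeks. Those ranges span both models: 2% to 10% stopping spread over 84 days, and 5% concentrated in the first 28. The direction is toward texters wherever the artefact exists; the size cannot be settled from the documents. It is a modest bias that is cheap to check, and it is separate from self-selection among repliers.

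**What to change.** In the texter definition (Measures and Data Collection) and in Data Analysis:

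1. Classify by authentication status at a fixed landmark after the first HCV dose, for example day 14, repeated at day 28. Those authenticated by then are texters; all others, including later authenticators, are non-texters. Restrict to patients still on treatment at the landmark, and apply the same landmark to comparison-clinic patients.
2. Report the delay from first dose to authentication, and the number who stopped before the landmark, by clinic type. If nearly all replies came at or before the first dose, this alone answers the point.
3. State how early stoppers enter the SVR denominator.
4. Alongside, compare all agreeing UI and AI patients with comparison-clinic patients regardless of texting. This removes the timing artefact and reply-based self-selection, and fits the role that the Design section gives the matched sites.

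The cost is a few lines of text and one date comparison per patient. Early stoppers leave the landmark comparison, late authenticators dilute it, and the clinic-level comparison is open to differences between clinics, with only two comparison clinics. Authentication and first-dose dates are not listed among the extracted data. The adherence denominator and the SVR timing suggest that texting and treatment dates exist, but their availability should be confirmed.
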